Short Title:	ATTUNE Cementless FB Tibial Base Clinical Study					
Protocol Number:	DSJ_2019_05					
	 h) Loss of bone or musculature, inadequate bone quality (e.g. severe osteoporosis), neuromuscular compromise or vascular deficiency at the bone site in the affected limb in sufficient degree to render the procedure unjustifiable (e.g. absence of musculoligamentous supporting structures that could lead to implant instability, joint neuropathy). i) Severe instability secondary to advanced loss of osteochondral structure or the absence of collateral ligament integrity. j) The inability to make bone cuts (e.g. inadequate bone stock) so as to assure correct component position, a firm press fit, and intimate apposition of the cut bone and prosthetic surfaces. k) Subject is currently involved in any personal injury litigation, medical-legal or worker's compensation claims. l) Subject, in the opinion of the Investigator, is a drug or alcohol abuser (in the last five 5 years) or has a psychological disorder that could affect their ability to complete patient reported questionnaires or be compliant with follow-up requirements. 					
Study Duration:	It is anticipated that recruitment for each configuration will be completed study-wide in 2.5 years. Follow-up is five (5) years. Therefore, the total planned study duration for each configuration is approximately seven and a half (7.5) years.					
Procedure Schedule	Subjects included in the investigation will be evaluated pre-operatively, at 6 weeks, 6 months, 1 year, 2 years and 5 years postoperatively. Subjects will also be contacted at 3 years and 4 years, but no detailed clinical assessments will be done at that time. See Table 1-1 Time & Events Table for details.					
Type and frequency of Adverse Events will be collected. Site Ethics Co (EC), Institutional Review Boards (IRB), and Regulatory Authorities wi oversight for study Subject safety. Safety A Data and Safety Monitoring board (DSMB) / Data Monitoring Committ / Critical Events Committee (CEC) will not be used for this trial. Routi review of Adverse Events and Serious Adverse Events will be conduct the study.						

Table 1-1: Time and Events Table

	Pre-op	Operative	6wk	6mo	1yr	2yr	3yr Contact	4yr Contact	5yr
Required	-180 to -1d		1d to 90d	91d to 303d	304d to 669d	670d to 1033d	1034d to 1398d	1399d to 1763d	1764d to 2044d
Preferred	-90d to -1d	Day 0	28d to 56d	166d to 194d	335d to 395d	670d to 790d	1065d to 1125d	1430d to 1490d	1795d to 1855d

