8.3.4 Adverse Event Reporting Guidelines

8.3.4.1 AE Reporting by Site to Sponsor

Subjects should be encouraged to report AEs spontaneously or in response to general, non-directed questioning (e.g. "How has your health been since your last visit?"). The Subject may volunteer information relating to AEs at any time during the Study. If an event occurs at an outside institution, the Investigator should attempt to obtain, if possible, required AE information.

All SAEs and all Device and/or Procedure-Related AEs must be reported to the Sponsor, regardless of classification, severity or outcome. The Investigator is responsible for ensuring that all protocol reportable

DSJ_2019_05, Rev D (FINAL) 24 August 2022

AEs observed by the Investigator (or designee), or reported by the Subject, that occur from the intraoperative time frame through to the end of the Study (either study completion or withdrawal of consent) are properly assessed, recorded and reported. All protocol reportable AEs must be documented in the study Subject's medical records (source documents) and reported in the database on the Adverse Event eCRFs. All AEs will be monitored until they are adequately resolved or explained. When a Subject ends participation in the study (either through study completion or consent withdrawal) an AE must be designated either as "resolved" (end date must be provided), or as "ongoing."

Table 8-7: Adverse Event Reporting Requirements to Sponsor

Type of Adverse Event	Reporting Requirements
SAEs (including SADEs, USADEs and	Report to Sponsor by completing an AE eCRF or by direct
ASADEs)	contact to Sponsor (i.e. via phone or e-mail) immediately
All Implant Device Deficiencies	upon awareness of event but no later than 72 hours.
(including those that potentially could	
have led to an AE/SAE*)	If related to an Implant/Instrument Device Deficiency, also
	complete a Device Deficiency eCRF as soon as possible but
	no later than 72 hours.
AE (Device and Procedure Related,	Report to Sponsor by completing an AE eCRF or by direct
including ADEs and UADEs). See Table	contact to Sponsor (i.e. via phone or e-mail) immediately
8.5 for further definition of AE	upon awareness of event but no later than 72 hours.
relatedness	
AEs related to a Device Deficiency	Report to Sponsor immediately upon awareness of event
	but no later than 72hrs, in line with Device Deficiency
	reporting requirement above.
All other AEs not listed above	Report to Sponsor within 2 weeks of awareness.

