9.6.2 Safety Analysis Set

The Safety analysis set consists of all ITT subjects who undergo surgery to implant the ATTUNE Cementless FB tibial base. Subjects who withdraw from the study prior to surgery will not be included in the Safety analysis set.

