9.8.1 General Conventions

All analysis will be performed using SAS v9.4 or higher. Statistical summaries (tallies and percentages for categorical variables, and sample size, mean, standard deviation, minimum and maximum (and others as needed) for continuous variables) at each respective time point, or cumulatively for safety endpoints.

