9.8.4.2 Secondary Endpoints and Associated Hypotheses

The secondary endpoints in this study are:

- Type and frequency of Adverse Events and Device Deficiencies.
 - Functional responder rates with an objective performance criteria (OPC) of 85% as measured by the KOOS questionnaire for all subjects (CR FB and PS FB combined) at the 1 year timepoint.
- The change from preoperative baseline to the 6 week, 6 month, 1 year, 2 year and 5 year timepoints in functional outcomes and quality of life assessments, as measured using additional patient reported outcomes measures (PROMS):
 - o AKS 2011
 - KOOS (all subscores)
 - FJS-12 (changes post-operatively only)
 - o *EQ-5D-5L*
- Implant survivorship of the ATTUNE Cementless FB Tibial Base using Kaplan-Meier survival analysis at 1, 2 and 5 year timepoints.
- Investigator-conducted radiographic analysis of the tibial and patellar components at 6 weeks/6 months, 1, 2 and 5 years after surgery.

All secondary endpoint analyses may be conducted after all patients have passed the recommended study window (ex. with a 2-year follow-up analysis conducted after all subjects have passed 790 days post-op). All analyses at these time points will be conducted again with final data, along with endpoints which have a 5-year follow-up time point, with locked data at the close of the study.

A Kaplan-Meier survivorship model will be used to estimate survivorship rates (where a revision is defined in Section 8.6) along with a two-sided, log-log based 95% confidence intervals; this analysis will be conducted on the Safety analysis set.

The types and frequencies of adverse events that occur throughout the study will be tabulated by MedDRA system organ class (SOC) and preferred term (PT) for all Subjects in the Safety analysis set. The proportion of Subjects experiencing each complication (PT within SOC) will be presented, and a 95% confidence interval will be estimated with the binomial exact method.

All other specified secondary endpoints will be presented with statistical summaries at each respective time point; these secondary endpoint analyses will be carried out with all data on subjects in the Per Protocol analysis set.

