9.8.5 Plans for Interim Analysis

There are no formal interim analyses planned with the intent of early trial closure.

Interim summaries may be performed as required, for example to provide information to Regulatory Authorities or Notified Bodies.

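### Adverse events over five years are summarised only as a crude proportion of all implanted subjects, which understates the risk by a fixed time for non-revision events that occur after the perioperative period

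*Combined protocol and SAP*

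**What the plan says.** Section 9.8.4.2 tabulates AEs by MedDRA class and preferred term on the Safety set: "The proportion of Subjects experiencing each complication (PT within SOC) will be presented". The same sentence gives the measure of precision: "a 95% confidence interval will be estimated with the binomial exact method". Section 9.6.2 fixes the denominator: "The Safety analysis set consists of all ITT subjects who undergo surgery to implant the ATTUNE Cementless FB tibial base". Section 9.8.1 has summaries made at each time point, "or cumulatively for safety endpoints". Section 8.3.4.1 collects reportable AEs that "occur from the intraoperative time frame through to the end of the Study", and the Summary states that "Follow-up is five (5) years".

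Subjects can leave earlier. Section 8.5 lists consent withdrawal, surgeon decision, death and revision, and excludes data after the withdrawal date. Section 8.6 withdraws subjects at femoral or tibial-base revision. Section 8.7 covers loss to follow-up. Section 9.5 rules out imputation.

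Revision is handled differently, on the same Safety set: "A Kaplan-Meier survivorship model will be used to estimate survivorship rates", with log-log 95% intervals. Section 9.8.5 adds: "Interim summaries may be performed as required, for example to provide information to Regulatory Authorities or Notified Bodies". It names no estimator for AEs in such summaries.

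**The concern.** A binomial proportion estimates the risk by a fixed time only if everyone in the denominator was observed to that time or had the event first. A subject lost at month 3 counts here as event-free for the whole five years. The plan avoids this for revision, but not for the other knee complications, some of which (osteolysis and polyethylene wear in Exhibit B) are typically late.

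The study has no control arm, so a shortfall cannot cancel in a comparison. Readers, including regulators, will tend to take each percentage as the absolute five-year risk and its interval as the uncertainty about that risk. Section 3.2 says the five-year follow-up was chosen partly to inform on the medium term, which is where the crude figure is weakest.

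**Working it through.** **The plan's own figure.** The documents state no AE rate, no AE precision and no five-year loss rate. The only attrition figure is in section 9.7: up to 15% at 1 year, used to size the primary endpoint. That calculation reproduces:

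- n = [(1.645 × √(0.85 × 0.15) + 0.842 × √(0.91 × 0.09)) / 0.06]² = 190.5, so 191.
- 191 / 0.85 = 224.7, so 225.

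It concerns a missing 1-year KOOS and is not a rate of loss for AEs, so loss by year 5 is varied below as an assumption.

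**Model.** Let R be the true five-year risk, T = 5, loss hazard c = −ln(1 − L)/5 for a proportion L lost by year 5, and loss independent of events. The expected crude proportion is:

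- Evenly spread events (constant hazard h = −ln(1 − R)/5): h/(h + c) × [1 − exp(−5(h + c))].
- Events uniform between times a and b: R × [exp(−ca) − exp(−cb)] / [c(b − a)].

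**One case in full.** For R = 10% and L = 15%, h = 0.02107 and c = 0.03250. The crude proportion is 0.02107/0.05358 × (1 − 0.90 × 0.85) = 0.3933 × 0.235 = 9.24%, which is 7.6% below 10% in relative terms.

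**Results for R = 10%.** Each cell gives the expected crude value, the relative shortfall, and the coverage of the true 10% by the exact 95% interval at N = 600.

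| Event timing | 15% lost | 25% lost | 30% lost |
|---|---|---|---|
| Evenly over 5 years | 9.24%, −7.6%, 92% | 8.71%, −12.9%, 84% | 8.44%, −15.6%, 77% |
| Between years 2 and 5 | 8.93%, −10.7%, 88% | 8.19%, −18.1%, 70% | 7.81%, −21.9%, 57% |
| First 90 days | 9.96%, −0.4%, 96% | 9.93%, −0.7%, 96% | 9.91%, −0.9%, 96% |

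The relative shortfall hardly depends on R: for evenly spread events it is 7.7% to 15.8% at R = 2% and 7.4% to 15.3% at R = 20%. Coverage does depend on R. At R = 2% it is still 96%, 94% and 94% for evenly spread events, because the interval is wide relative to the bias.

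**Timing of loss.** If the 15% all leave in year 1 and nobody leaves later, R = 10% with constant hazard gives 8.65%, a shortfall of 13.5%. Early loss costs more than the same loss spread over five years.

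**Staggered entry.** At the final analysis every subject has the same planned five years, so entry date does not matter. It matters only for an interim table. As an illustration, assume 600 implants spread evenly over 2.5 years and a cut when the 225th passes day 395:

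- The cut falls at 225/600 × 2.5 + 395/365.25 = 2.02 years.
- About 2.019/2.5 × 600 = 485 knees are then implanted, and 1/2.019 = 50% of them have under one year.
- If all were pooled, a true 1-year risk of 10% would show as 7.6%, with constant hazard and no other loss.

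**The case against.** **The endpoint is descriptive.** The objective is the type and frequency of AEs, and an exact interval is valid for an observed frequency. This stands. The interval fails only as a statement about risk by a fixed time, but the plan does not label the table to prevent that reading.

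**Other analyses cover part of the ground.** Revision has Kaplan-Meier, and Exhibit B defines osteolysis and wear as seen on radiographs or at revision, with radiographic analysis planned separately. This also stands, and it limits the point to AEs other than revision.

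**A reader might infer that all AE risk in this study is biased low.** The documents do not support that. Events in the first 90 days lose under 1%, and section 3.2 itself identifies the first year as the time when initial fixation problems may become evident.

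**A reader might take the 15% in section 9.7 as loss for AEs.** It is an upper allowance for the primary endpoint. A subject without a 1-year KOOS may still report AEs: Table 1-1 accepts them by phone or mail, and the year 3 and 4 contacts exist partly to capture them.

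**A reader might infer that the 225-knee submission will report AE rates diluted by recent implants.** Sections 7 and 9.8.4.1 assign only the primary endpoint to that cut. Section 9.8.4.2 places secondary analyses after all patients have passed the window. Section 9.8.5 would allow such a table but does not describe one, and even accrual is an assumption.

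**A reader might count death and mandatory withdrawal at revision as sources of the bias.** Treated as competing events, they do not bias a crude proportion as an estimate of cumulative incidence. The bias comes from loss, consent withdrawal and surgeon withdrawal.

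**Conclusion.** The concern holds in a limited form. For AEs other than revision that occur after the perioperative period, the planned proportion and its interval sit below the fixed-time risk. With an assumed 15-30% lost by year 5, the relative shortfall is about 8-16% for evenly spread events and 11-22% for events between years 2 and 5. It is negligible for early events. For uncommon terms the interval remains nearly adequate; coverage suffers mainly for more frequent or late events.

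These figures rest on the assumed loss rates, on loss unrelated to events, and on simple event timing. The direction follows from the estimator whenever subjects leave before an event they would have had. The primary endpoint is unaffected. This is an inexpensive improvement to the safety reporting, not an error in the crude table as description.

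**What to change.** - Keep the crude table by system organ class and preferred term, and label it as observed frequency.
- For serious AEs, device- or procedure-related AEs and the Exhibit B knee complications, add cumulative incidence at 1, 2 and 5 years with 95% intervals and numbers at risk.
- Use the Aalen-Johansen estimator with death and tibial or femoral revision as competing events. Plain Kaplan-Meier would censor these as if the event could still happen, and so overstate the risk. Subjects who are lost or withdrawn for other reasons are censored at their last contact for AEs.
- Name the same estimator in section 9.8.5 for any interim AE summary sent to regulators, so that short follow-up is handled there too.

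Onset dates are already on the AE eCRF (Table 8-1), so no new data are needed. The cost is SAP wording, a few more tables and slightly less favourable late-event rates. The estimator still assumes that loss is unrelated to AE risk, and the report should say so.

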9.4 Levels of Significance

Where estimated, all confidence intervals will be 95% confidence intervals. For the primary endpoint hypothesis test an alpha = 0.05 will be used to determine statistical significance. No adjustments will be made for multiplicity as this is the only hypothesis in the study.

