9.7 Sample Size Justification

The primary endpoint in this study will be to estimate the Functional Responder (defined below in Section 9.8.4.1) rate at 1 year and demonstrate superiority to the 85% objective performance criteria. Functional Responder rates are anticipated to be between 91-94% in primary TKA based on a previous study of ATTUNE Cemented and ATTUNE Cementless CR RP knees. Using the lowest anticipated rate of 91%, a sample size of 191 knees will provide at least 80% power to show superiority of the Functional Responder rate compared to the objective performance criteria of 85%, with 95% confidence using a one-sided, normal approximation, one-proportion test and associated confidence interval. Accounting for up to 15%

DSJ_2019_05, Rev D (FINAL) 24 August 2022 DePuy Synthes Products, Inc. - Confidential

attrition at 1 year, the sample size population for analysis of the primary endpoint was increased to the first N=225 knees enrolled.

Due to various global requirements and anticipated regulatory submissions the sample size is increased to N=300 per configuration.

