9.8.4.1 Primary Endpoint and Associated Hypotheses

The primary endpoint is the Functional Responder Rate (FRR) at 1 year. A Functional Responder is defined as:

- A subject that shows at least 20% improvement from baseline and at least a 10-point improvement from baseline in at least 2 of the following categories:
 - o KOOS (ADL)
 - o KOOS (Pain)
 - o KOOS (Quality of Life)

Functional Responder rates are expected to be between 91%-94%. The objective performance criteria for study success is 85%.

$$H_0$$
: FRR $\leq 85\%$

$$H_A: FRR > 85\%$$

The primary endpoint will be performed on the first 225 tibia implanted with the ATTUNE Cementless FB tray (primary and revision procedures, CR FB and PS FB combined) and will be analyzed when these patients have passed the 1 year preferred post-op window (395 days). This analysis will be done on the Per Protocol (PP) population. Study success will be determined using the primary TKA (CR FB and PS FB combined) analysis group.

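### The all-subject 1-year responder rate is set against an 85% criterion, but its only planned analysis is a count and percentage, which cannot show that the rate exceeds 85%

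*Combined protocol and SAP*

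**What the plan says.** Section 9.8.4.2 includes among the secondary endpoints "Functional responder rates with an objective performance criteria (OPC) of 85% as measured by the KOOS questionnaire for all subjects", CR and PS fixed bearing combined, at 1 year. The synopsis, Section 6.2 and Table 6-1 carry the same endpoint with the same 85%, so the benchmark is deliberate.

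The section then assigns analyses. Survivorship gets a Kaplan-Meier estimate with a two-sided log-log 95% interval. Adverse-event proportions get an exact binomial 95% interval. For everything else, "All other specified secondary endpoints will be presented with statistical summaries at each respective time point", on the Per Protocol set. Section 9.8.1 describes those summaries as "tallies and percentages for categorical variables"; its allowance for further statistics as needed sits in the list for continuous variables.

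Section 9.4 sets a level but does not call for an interval on this endpoint: "Where estimated, all confidence intervals will be 95% confidence intervals". It also treats the primary test as the only one: "No adjustments will be made for multiplicity as this is the only hypothesis in the study". The one-sided normal-approximation test and its interval in Section 9.7 belong to the primary endpoint. Section 9.8.4 adds that each endpoint is analyzed for all knees and separately for primary and revision procedures and by configuration.

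**The concern.** A performance criterion asks whether the true rate is above a fixed value. An observed percentage answers that only together with a statement of its uncertainty. The primary endpoint has this: a null hypothesis of 85% or less, a one-sided test and alpha of 0.05. The secondary endpoint names the same 85% and has none of it. Within one section, every adverse-event proportion gets an interval, while the only secondary proportion that carries a benchmark does not.

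This will be the study's largest responder analysis, and Section 3.1 says the data are meant for CE mark registration in Europe and for other regions. A full-cohort percentage reported next to 85% invites a pass-or-fail reading, and the plan gives no rule for how it should be read.

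**Working it through.** **Inputs.** OPC 85%, lowest anticipated rate 91%, one-sided 95% confidence, 80% power and up to 15% attrition (Section 9.7); at least 600 subjects (Section 9.1); no imputation (Section 9.5). The evaluable number for the secondary endpoint is not stated. I assume 600 × 0.85 = 510 and check 480 to 600.

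**1. The plan's own figure.** For the primary endpoint,

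n = [1.645 × √(0.85 × 0.15) + 0.842 × √(0.91 × 0.09)]² / 0.06² = 190.5, rounded up to 191, with power 80.1%.

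Then 191 / 0.85 = 224.7, rounded up to 225. Both stated figures reproduce and are not at issue. The plan states no figure for the secondary endpoint.

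**2. Percentage alone.** With 510 knees, 0.85 × 510 = 433.5, so 434 responders put the observed rate above 85%. With 600 knees, 85% is exactly 510, so 511 are needed. Exact binomial tail probabilities:

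| True rate | P(X ≥ 434), n = 510 | P(X ≥ 511), n = 600 |
|---|---|---|
| 85% | 50.6% | 48.3% |
| 84% | 27.2% | 23.6% |
| 83% | 11.3% | 8.5% |

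At n = 600, counting exactly 85% as reaching the mark raises 48.3% to 52.8%. At the sizes checked from 480 to 600, the figure at a true 85% stays between about 48% and 51%, so the result does not depend on the assumed 510.

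**3. With a lower bound that must exceed 85%, n = 510.** For the normal-approximation test with the null variance, the cut-off is 0.85 + 1.645 × √(0.85 × 0.15 / 510) = 0.876, and 0.876 × 510 = 446.8, so 447 are needed. The other methods differ slightly:

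| Lower bound | Responders needed | Cleared if true rate 85% | Cleared if true rate 91% |
|---|---|---|---|
| One-sided 95%, Wald | 446 (87.5%) | 6.6% | 99.7% |
| One-sided 5% test, null variance | 447 (87.6%) | 5.1% | 99.5% |
| One-sided 95%, exact | 448 (87.8%) | 3.9% | 99.3% |
| Lower limit of two-sided exact 95% interval | 450 (88.2%) | 2.1% | 98.6% |

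For the null-variance test, the chances at true rates of 84% and 83% are 1.2% and 0.2%. At n = 600, the null-variance test and the one-sided exact bound both need 525 (87.5%), with 4.6% at a true 85% and 99.8% at 91%.

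**4. The results affected.** At n = 510 with a one-sided 95% bound, the largest count that lies above 85% without showing it is 445 (87.3%), 446 (87.5%) or 447 (87.6%), depending on the method. The range starts at 434 (85.1%).

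**The case against.** The strongest reply is that the plan makes no decision on this endpoint. Section 9.4 recognizes one hypothesis, and Section 9.8.4.1 says "Study success will be determined using the primary TKA (CR FB and PS FB combined) analysis group". A reader might infer that the 51% is a false-positive rate for a secondary claim. The documents do not support that: nowhere do they say that an all-subject rate above 85% counts as success. This part of the objection stands, and the figure is only the chance of appearing to meet the criterion.

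A second reply is that a count and a denominator let anyone compute an interval, and that Section 9.4 fixes its level if one is shown. That is true, but it leaves the method, and the reading against 85%, to be chosen once the data are known. Part 3 of the working shows that the required count moves with the method.

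A third reply is that the ambiguous range hardly matters if the device performs as expected: at a true 91%, the chance of landing there is about 0.5% under the null-variance test. This also stands and limits the practical weight. The gap matters when the true rate is near 85%, which is where a criterion has to discriminate.

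A reader might also infer that pooling revision procedures makes the 85% comparison invalid. The documents do not support that either. Section 9.7 says "Functional Responder rates are anticipated to be between 91-94% in primary TKA", but as the anticipated rate for the sample size, not as the basis for 85%. Section 9.8.4 already plans separate primary and revision results. The plan gives neither a revision share nor a revision responder rate, so the effect of case mix cannot be sized from it.

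**Conclusion.** The point holds as a gap in the analysis of one secondary endpoint. The plan names a performance criterion and specifies an analysis that cannot show whether it is exceeded. Under the assumed 510 evaluable knees, a device whose true rate equals the criterion would show an observed rate above it about half the time, and one at 84% about a quarter of the time. The half-the-time figure holds across the range of sizes checked.

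The primary endpoint, its sample size and the study success rule are unaffected. Nothing here implies that the plan would declare success on a bare percentage. The change is worth making because it costs almost nothing and settles the reading before the results are known.

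**What to change.** In Section 9.8.4.2, state that the all-subject 1-year responder rate, and the separate primary-TKA and revision rates already planned in Section 9.8.4, are reported with confidence intervals from one named method. Two choices fit the plan: the one-sided 95% lower bound used for the primary endpoint, or the exact binomial method already used for adverse events. If the first is chosen, name the form, because Section 9.7 says only normal approximation. If the second, say whether the one-sided bound or the lower limit of the two-sided interval is read against 85%.

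Add that a rate is described as exceeding the OPC only if its lower bound is above 85%, and that this is supportive and descriptive with no effect on study success. With that label, the statement in Section 9.4 that there is only one hypothesis can stand. If the sponsor wants a formal test instead, Section 9.4 would have to be revised.

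The cost is a few sentences in the plan and interval columns in an existing table, with no more patients or data. The downside is that observed rates just above 85%, up to roughly 87.3% to 87.6% at 510 knees with a one-sided 95% bound (449/510 = 88.0% with the two-sided exact interval), could no longer be described as exceeding the OPC. At the planned 91%, the bound would still be cleared about 99% of the time.
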